3 OBJECTIVES AND ENDPOINTS

The primary outcome measurement for effectiveness is:

-The difference between the active and sham treatment groups in mean daily morphine equivalence dosage during study

Secondary endpoints include descriptive comparisons between the active and sham treatment groups in:

- The difference in mean daily headache intensity during the study

The difference between total overall morphine equivalence dosages per subject during study
 Opiate related adverse events (such as urinary retention, constipation, sedation, nausea, vomiting and pruritis)

- The difference in cytokines levels and brain permeability markers in the blood and/or CSF before and after stimulation and between the sham and active device group

- Effects of VNS on brain permeability measured through CT perfusion studies

-The difference in modified rankin scale at hospital discharge and during outpatient follow up. This will be collected retrospectively from the follow up outpatient visit.

Exploratory analyses will include descriptive comparisons of the rates of stroke, vasospasm, DCI, seizure, central fever and severity of vasospasm between the active and sham treatment groups.

OBJECTIVES	ENDPOINTS
Primary Objective:	

Incidence of device related serious adverse events.	Proportion of patients with device related adverse events
The difference between the active and sham treatment groups in mean daily morphine equivalence dosage during study	Morphine equivalence dosage will be calculated per day.
Secondary Objectives	
The difference between the active and sham treatment groups in the mean daily headache intensity during the study	Headache intensity will be measured throughout the day and a mean daily headache intensity will be calculated.
The difference between total overall morphine equivalence dosage between the active and sham group per subject during study	Total morphine equivalence dosage for the duration of the study will be calculated.
Incidence of opiate related adverse events (such as urinary retention, constipation, sedation, respiratory depression, nausea, vomiting and pruritis)	Number of patients with of urinary retention, constipation, sedation, nausea, respiratory depression, vomiting and pruritis.

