9 STATISTICAL CONSIDERATIONS

9.1 STATISTICAL HYPOTHESES

There are no statistical hypotheses in this study. This is a feasibility pilot study that will allow us to better calculate the sample size for a large randomized control study comparing VNS to sham device.

The primary outcome measurements for effectiveness will be:

-The difference between the active and sham treatment groups in mean daily morphine equivalence dosage during the study period

Secondary endpoints include descriptive comparisons between the active and sham treatment groups in:

- The difference between the active and sham treatment groups in mean daily headache intensity during the study period

- The difference between total overall morphine equivalence dosage between the active and sham group per subject during study

-Opiate related adverse events (such as urinary retention, constipation, sedation, nausea, vomiting and pruritis)

Exploratory analyses will include comparisons of the rates of stroke, vasospasm, DCI, seizure, central fever and severity of vasospasm between the active and sham treatment groups.

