Title: Safety and efficacy of non-invasive Vagus Nerve Stimulation (nVNS) in the treatment of headache in Subarachnoid Hemorrhage (SAH)

MAY, 1, 2022

NCT04126408

Overview of study design

This is a single site, randomized, sham-controlled, double-blind study assessing the feasibility, safety, tolerability, and efficacy of non-invasive VNS (nVNS) in the treatment of headache in subarachnoid hemorrhage (SAH).

We hypothesize that two two-minute noninvasive stimulations of the cervical branch of the Vagus nerve, every 5 hours, is efficacious in safely reducing headache intensity and frequency in patients with headache due to SAH, during the patient's intensive care unit (ICU) stay.

After screening and obtaining informed consent, eligible patients diagnosed with SAH on head scans, admitted to the Neurosurgical Intensive Care Unit (NSCU) at Northshore University Hospital will be randomized to either the treatment (stimulation of the cervical branch of the Vagus nerve) or sham (inactive stimulation) group.

Pain intensity will be evaluated every 4 hours. Non-invasive stimulation will be performed every 5 hours.

The treatment arms are the following:

Group 1: Control (patients will receive treatment using an inactive VNS device)

Group 2: Treatment (patients will receive treatment using an active VNS device)

The patients are randomized with equal probability to one of the treatment arms. In total, approximately 40 patients will be recruited

Primary objective

The primary objective of this study is to evaluate the effectiveness of VNS compared to sham device as measured by the mean daily morphine equivalence dosage during the study

Secondary Objectives

The secondary objectives of the study are to compare VNS to sham treatment with respect to effects on the following:

- total overall morphine equivalence dosage
- mean daily headache intensity during the study
- cytokines levels
- blood brain permeability markers in the blood and/or CSF before and after stimulation
- blood brain barrier integrity

Exploratory objectives:

- stroke, vasospasm, DCI, seizure, and central fever
 - The presence of DCI,
 - Transcranial doppler velocity,
 - The number of days with central fever,
 - Incidence of seizures
- severity of cerebral vasospasm during DSA

Safety objectives:

- Opiate related adverse events (such as urinary retention, constipation, sedation, nausea, vomiting and pruritis)
- Occurrence of Adverse Events (AEs)/Serious Adverse Events (SAEs)
- Vital Signs

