- Rate of side effects:
 - o presence of intolerable pain at the stimulation site,
 - o skin irritation,
 - o nasopharyngitis,
 - o hoarseness,
 - o dysgeusia,
 - o shortness of breath,

Outcome measures

Primary efficacy variable:

The daily morphine equivalency dosage by visit

Secondary efficacy variables:

- total overall morphine equivalence dosage
- mean daily headache intensity during by visit
- cytokines levels
- blood brain permeability markers in the blood and/or CSF before and after stimulation
- blood brain barrier integrity

Exploratory variables:

(Stroke, vasospasm, DCI, seizure, and central fever)

- The presence of DCI,
- Transcranial doppler velocity,
- The number of days with central fever,
- Incidence of seizures)
- severity of cerebral vasospasm during DSA

Safety variables:

Opiate related adverse events

- urinary retention,
- constipation,
- sedation,
- nausea,
- vomiting and
- pruritis
- Occurrence of Adverse Events (AEs)/Serious Adverse Events (SAEs)

Rate of side effects: presence of intolerable pain at the stimulation site,

- skin irritation,
- nasopharyngitis,
- hoarseness,
- dysgeusia,

- shortness of breath,
- Vital Signs (weight, BMI, SBP, DBP, and pulse rate are collected at each day)

Statistical considerations

Sample size determination

There are no statistical hypotheses in this study, and therefore there is no sample size justification for this study. This is a feasibility pilot study that will allow us to better calculate the sample size for a large, randomized control study comparing VNS to sham device.

General approach:

- Baseline is defined as the value measured at visit 1 (Day 1). Endpoint is defined as last observed value during visit 14 (Day 14).
- Missing efficacy. Two statistical approaches to handling missing data will be performed in this study.
 - The primary analysis will be a repeated measures analysis of the primary efficacy endpoint. Estimates have been shown to be unbiased when the missing data are missing completely at random and when there is ignorable nonrandom missing data.
 - A secondary analysis will utilize an LOCF analysis
- All statistical tests for treatment difference will be 2-sided and conducted at the 0.05 level of significance.

Analysis populations

The following analysis sets will be used for the statistical analysis and presentation of data:

- ITT: All randomized participants will be included in the Intent To Treat (ITT) population.

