The primary efficacy variable, the daily morphine equivalency dose by visit, will be analyzed using a restricted maximum likelihood (REML)-based repeated measures approach (Mixed Model Repeated Measures (MMRM)). The model for analysis will include fixed, categorical effects of treatment, visit, and treatment by visit interaction, as well as the continuous, fixed covariates of baseline value. An unstructured (co)variance structure will be used to model the within-patient errors. If this analysis fails to converge, compound symmetry will be tested. The (co)variance structure converging to the best fit, as determined by Akaike's information criterion will be used as the primary analysis. The Kenward-Roger approximation will be used to estimate denominator degrees of freedom. The primary treatment comparison will be the contrast between treatments at Day 14 for active treatment versus sham treatment. Treatment group differences contrasts will be computed overall and for each analysis visit (i.e., Day 1, Day 2, Day 3, ..., Day 14) and displayed with the respective 95% CIs. Significance tests will be based on least-squares means and Type III sum-of-squares, using two-sided tests at the 0.05 level (two-sided 95% confidence intervals). No imputed values will be used for the MMRM analysis.

Sensitivity analysis

All analyses on the primary efficacy endpoint will be repeated on the PPS

Additionally, the missing data for the mean daily morphine equivalency dose will be computed using an LOCF algorithm and analyzed using the MMREM model.

Analysis of Secondary and Exploratory Variables

For each of the variables mentioned above, the randomization group difference will be examined using a T-test for continuous variables, and Fisher's exact test for categorical variables at each visit.

Analysis of safety variables

Treatment group differences in the occurrence of serious adverse events will be evaluated using Fisher's exact test.

Adverse events:

The primary safety endpoint of this study is the overall incidence of device related serious AEs. AEs and SAEs will be summarized and presented as proportions and respective 95% exact binomial confidence intervals (CIs).

Frequency and percentage of subjects experiencing a specific adverse event will be tabulated by system organ class, preferred term, and treatment group.

Summary tables and subject data listings will be provided.

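### The SAP's primary comparison is the Day 14 contrast, but both documents define the primary endpoint as mean daily morphine equivalents over the study, and Day 14 is not reconciled with the up-to-10-day period

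*SAP*

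**What the plan says.** Protocol section 3 gives the primary effectiveness outcome as "The difference between the active and sham treatment groups in mean daily morphine equivalence dosage during study". Section 9.1 repeats it as a difference "in mean daily morphine equivalence dosage during the study period". The SAP's primary objective agrees: effectiveness is to be judged "as measured by the mean daily morphine equivalence dosage during the study".

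Under Outcome measures, the SAP words the primary efficacy variable as "The daily morphine equivalency dosage by visit". The Efficacy Analysis section fits an MMRM with treatment, visit, their interaction and the baseline value, and then says: "The primary treatment comparison will be the contrast between treatments at Day 14 for active treatment versus sham treatment". It adds: "Treatment group differences contrasts will be computed overall and for each analysis visit", listing Days 1 to 14 with 95% confidence intervals. The overall contrast is not called primary and its days are not defined. Under General approach, the SAP sets baseline at visit 1 (Day 1), the endpoint at visit 14 (Day 14), and all treatment tests at the two-sided 0.05 level.

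The protocol puts the study period, intervention, follow-up or treatment period at up to 10 days (Synopsis, 4.4, 5.5, 7.3, 8.1). It never mentions Day 14. Data collection runs to hospital discharge (4.4).

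**The concern.** If the SAP is followed to the letter, the one test labelled primary answers whether the arms differ on Day 14. Both documents ask whether they differ in mean daily opioid use over the study. A benefit confined to the stimulation period could be missed, and a late difference could stand in for a study-long one.

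Day 14 may also lie after the last stimulation. By then, observed values come only from patients still in hospital. The primary (mITT) set requires 7 treated days, so a patient can belong to it and have no Day 14 value. For those patients the MMRM relies on earlier days and a missing-at-random assumption.

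**Working it through.** The documents give no effect size, variance or power, so there is no figure of the plan's own to reproduce. The check is a comparison of text, followed by illustrations whose inputs are assumptions.

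**1. What each quantity is.** Let δ(d) be the active-minus-sham difference in mean daily dose on day d.

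- SAP primary comparison: δ(14).
- Stated endpoint: the average of δ(d) over the m days of the study period, (1/m) Σ δ(d).

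The interaction term lets δ(d) vary freely by day, so the two agree only in special cases, such as a constant effect. Two assumed shapes, taking Day 1 as baseline and a period ending on Day 10:

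- Effect 1 on Days 2–10, then 0: δ(14) = 0 and the Days 2–10 mean = 1. Over Days 2–14 the mean is 9/13 = 0.69.
- Effect rising as (d − 1)/13: δ(14) = 1 and the Days 2–10 mean = 5/13 = 0.38.

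**2. Where Day 14 falls.** With Day 1 as baseline, ten days are Days 1–10 or 2–11, so Day 14 is 4 or 3 days later. In general, a period starting on numbered day s has its tenth day on s + 9, so it reaches Day 14 only if s is 5 or more. There are routes to that:

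- Days numbered from aneurysm treatment, with enrolment on day 5 (4.1 allows days 1 to 5) and ten days counted from enrolment: 5 + 9 = 14.
- Days numbered from ictus or diagnosis, with treatment up to about 3 days later (5.5) and a start 24 hours after that. Day 1 would then precede enrolment, which sits badly with Day 1 as visit 1 and baseline. The figure in 8.2 stops at day 10 post-ictus.
- Held days (4.4, 7.1) not counted, and a patient having 3 or 4 of them.

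The SAP adopts none of these, and the documents do not say how often each would occur. Day 14 is unreconciled, not impossible.

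**3. Precision (illustration).** Assumptions: compound symmetry (the SAP's fallback structure) with correlation ρ, baseline as covariate, covariance treated as known, a fraction f of each arm observed to Day 14 and the rest to Day 10. In units of the daily variance, after conditioning on Day 1:

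- Variance of one day: 1 − ρ²; covariance between days: ρ(1 − ρ).
- Variance of the Days 2–10 mean: (1 − ρ)(1 + 9ρ)/9.
- Part of the Day 14 variance explained by Days 2–10: E = 9ρ²(1 − ρ)/(1 + 9ρ).
- Variance of the Day 14 estimate: (1 − ρ² − E)/f + E.

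All are divided by arm size, which cancels in the ratio. Example with ρ = 0.5 and f = 0.4: E = 0.2045; Day 14 variance = 0.5455/0.4 + 0.2045 = 1.568; variance of the mean = 0.5 × 5.5/9 = 0.3056; ratio of standard errors = √(1.568/0.3056) = 2.27.

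SE(Day 14) / SE(Days 2–10 mean):

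| Observed to Day 14 | ρ = 0.3 | ρ = 0.5 | ρ = 0.7 |
|---|---|---|---|
| 100% | 1.78 | 1.57 | 1.45 |
| 80% | 1.95 | 1.70 | 1.56 |
| 60% | 2.22 | 1.91 | 1.73 |
| 40% | 2.67 | 2.27 | 2.03 |

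Ending the period on Day 11 barely changes this: 1.80/1.58/1.46 with all observed, 2.70/2.28/2.04 at 40%. An AR(1) structure with correlations 0.5/0.7/0.9 gives 1.92/1.61/1.58 and 3.03/2.51/2.19. Under compound symmetry, a Days 2–14 mean has 0.96 to 1.02 times the standard error of the Days 2–10 mean, so the exact window matters little for precision.

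**The case against.** Both documents disclaim statistical hypotheses and describe a feasibility pilot. The overall and daily contrasts will be reported with confidence intervals whatever Day 14 is called, so no information is lost. The SAP's primary variable is worded by visit, and the protocol's endpoint column speaks only of a dose calculated per day, so mean daily might be read as a group mean of daily doses. The SAP is dated 1 May 2022 and protocol version 6 is dated 12 January 2023, so the period in force when the SAP was written cannot be seen. The precision ratios compare two different quantities, under assumed correlations, with covariance treated as known, whereas the SAP's first choice is unstructured.

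Most of this limits the size of the fault without removing it. The SAP does name one comparison as primary and does set a 0.05-level test. Leaving the choice among Day 14, an undefined overall contrast and other days until results are known would invite selection. Wording by visit describes the variable; the objective supplies the summary, and a measure taken during the study does not point to one day. The dates may explain the mismatch but do not resolve it. The caution on the ratios stands: they are illustrations, and they translate into an effective sample size only if the effect is the same on every day.

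**Conclusion.** The concern holds. The SAP's designated primary contrast does not target the endpoint that both documents state, however days are numbered; the two coincide only in special cases such as a constant effect. That conclusion rests on the text alone. Separately, Day 14 is not reconciled with the up-to-10-day period.

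The consequence depends on the unknown shape of the effect: in the two examples the Day 14 contrast is 0 against a mean of 1, or 1 against a mean of 0.38. The loss of precision, about 1.5 to 2.7 times the standard error across the compound-symmetry cases, depends on assumed correlation and on the share still observed on Day 14. The documents give an NSCU stay of 2–21 days but no hospital stay. The fault is confined to which contrast carries the primary test and over which days. It should be corrected before the analysis.

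**What to change.** 1. Define Day 1 once, and have the sponsor reconcile the SAP's 14 days with the protocol's up-to-10-day period, stating whether held days count.
2. Make the primary comparison the equally weighted average of the active-minus-sham least-squares-mean differences over the post-baseline days of the confirmed period. Name those days in the SAP and align its endpoint definition. In effect this gives the overall contrast already planned defined days and primary status. Other weightings are possible, but one must be fixed in advance.
3. Ask the sponsor to reconcile the study-period wording (protocol sections 3 and 9.1, SAP primary objective) with the NSCU-stay window in protocol 9.4.2 and 9.4.3 and the ICU-stay hypothesis in both documents, then use one window throughout. Opioid doses are already collected after step-down (1.2, 8.1), so either answer is feasible.
4. Keep Day 14 and the other daily contrasts as supportive.

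The cost is SAP wording and possibly a line each in protocol 9.4.2 and 9.4.3, with no new data or patients. There are two downsides. The late time point is no longer primary. The average still relies on modelled values for patients discharged before the period ends, so selection by discharge is reduced, not removed.

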The difference in cytokines levels and blood brain permeability markers in the blood and/or CSF before and after stimulation and between the sham and active group	When possible, cytokines levels and permeability markers will be measure in the blood and/or serum just before the first vagus nerve stimulation and approximately 24 hours later, after the 11:30 AM stimulation session. If possible, this will be repeated on day 5 and 7 post-ictus as it is the period of cerebral vasospasm

	Immunologic investigations include but not limited to, measurement of inflammatory protein levels, RNA		
	sequencing of leukocyte and stimulation assays.		
Evaluate the effects of VNS on	The integrity of the blood brain barrier will be evaluated		
blood brain barrier integrity	through CT perfusion if performed as standard of care.		
Exploratory objectives			
Comparisons of the rates of stroke, vasospasm, DCI, seizure, and central fever between the active and sham treatment groups	Neuroimaging upon admission and at discharge will be compared and evidence of new strokes will be noted. The presence of DCI (change in neurologic examination thought to be due to vasospasm) will be evaluated.		
	Transcranial doppler velocities will be compared between the active and sham groups		
	The number of days with central fever will be compared between the active and sham groups		
	Incidence of seizures will be compared between the active and sham groups		
Effect of nVNS on severity of cerebral vasospasm during DSA	Rate of change in the severity of cerebral vasospasm will be noted before and during or after nVNS		

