- Constipation evaluated by the need for enema, suppository, lactulose or magnesium oxide administered
- Blood tests, CSF studies
- EEG results
- Neurologic examination including Glasgow coma score, and NIHSS
- Delirium score

When Transcranial dopplers are being done as per standard of care, we will assess the changes in transcranial velocities around the time of the stimulation of the Vagus nerve.

When possible, we will draw blood or in case there is an EVD we will also collect CSF for biomarkers. Not more than 5 ml of blood will be drawn before the 11:30 am stimulation session of the Vagus nerve. This will be repeated approximately 24 hours later, at 11:30 am post VNS stimulation session. This might be repeated on days 5 and 7 post-ictus In case there is an EVD, 2 cc of CSF from the drain and 20 cc of CSF that is otherwise discarded will be drawn before the 11:30 am stimulation session of the Vagus nerve. Another 2 cc of CSF from the drain and 20 cc of CSF that is otherwise discarded will be drawn before the 11:30 am stimulation session of the Vagus nerve. Another 2 cc of CSF from the drain and 20 cc of CSF that is otherwise discarded will be drawn approximately 24 hours later, at around 11:30 am post VNS stimulation session. This might be repeated on days 5 and 7 post-ictus.

The CSF will not be taken from the proximal port of the EDV unless it is being tested for CSF cell count or cultures as per standard of care. This is in order not to increase the risk of infection.

Deidentified blood and CSF will be sent to [name], academic chief in the department of stroke and vascular neurology, Yale, [name].

IF CT perfusion is being performed per standard of care between days 3-10, blood brain permeability will be evaluated and results will be compared between the sham group and the active device group.

During the period of the study after the patients are discharged from the ICU to the Neurosurgical floor, we will evaluate their daily headache intensity and morphine equivalence dosage, in addition to their TCD results, Neuroimaging and EEG results, neurologic examination and vital signs.

Table 2: Hunt-Hess Score in aneurysmal SAH: (26, 27)

- 1. Asymptomatic, mild headache, slight nuchal rigidity
- 2. Moderate to severe headache, nuchal rigidity, no neurologic deficit other than cranial nerve palsy
- 3. Drowsiness, confusion, mild focal neurologic deficit
- 4. Stupor, moderate-severe hemiparesis
- 5. Coma, decerebrate posturing

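### For the cytokine and permeability biomarkers the SAP specifies only between-arm t-tests at each visit; no test or model uses the patient's pre-stimulation value, so the before/after change is at most summarised

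*SAP*

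**What the plan says.** Protocol section 3 lists among the secondary endpoints a comparison of "cytokines levels and brain permeability markers in the blood and/or CSF before and after stimulation and between the sham and active device group". Its objectives table places the samples "just before the first vagus nerve stimulation and approximately 24 hours later, after the 11:30 AM stimulation session", with possible repeats on days 5 and 7 after the bleed. The SAP carries the endpoint into its secondary efficacy variables as "blood brain permeability markers in the blood and/or CSF before and after stimulation"; cytokines are a separate item there, without the before/after wording.

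For analysis, the SAP section on secondary and exploratory variables gives one rule: "For each of the variables mentioned above, the randomization group difference will be examined using a T-test for continuous variables", with Fisher's exact test for categorical variables, at each visit. Protocol section 9.4.3 covers headache intensity, total morphine dose and opiate-related events, and gives no biomarker method. The baseline value enters as a covariate only in the SAP's mixed model for the primary endpoint.

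Two general statements in the SAP also bear on this. Under patient characteristics, changes from baseline are to be summarised where that applies. Under the general approach, baseline is the Day 1 value at the first visit.

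**The concern.** The endpoint has two parts: a change within the patient and a contrast between arms. A t-test of the arms at each visit addresses only the second. At the pre-stimulation time it compares the arms before any treatment and says nothing about the device. At the later time it ignores what is already known about each patient from the first sample.

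At stake is precision in a trial of about 40 patients, where biomarker sampling is opportunistic. The stated before/after change would also have no planned estimate with a confidence interval. Neither harms the primary analysis, but the first sample is drawn for this purpose and its main statistical use is not planned.

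**Working it through.** **1. What links the two samples.**

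| Place | What it provides | Uses the pre-stimulation value? |
|---|---|---|
| SAP, secondary and exploratory variables | t-test between arms at each visit | Not stated |
| SAP, primary efficacy model | Baseline as covariate | Morphine dose only |
| SAP, patient characteristics | Changes from baseline summarised where applicable | Possibly, descriptively, from a Day 1 value |
| SAP, vital signs and laboratory tests | Changes from baseline summarised | Biomarkers not named |
| Protocol 9.4.3 | Other secondary endpoints | No biomarker method |

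So no test or model is specified that uses the value. Whether even the descriptive change would use it is unclear, because neither document says that the Day 1 value is the pre-stimulation sample.

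**2. Inputs for sizing.** The plan states no power, effect size, SD or correlation, so there is no figure of its own to reproduce. From the documents: about 40 patients, 1:1, hence 20 per arm at most; two-sided 0.05; secondary variables analysed in the modified ITT set only, which requires at least 7 treated days; and collection on this footing: "When possible, we will draw blood or in case there is an EVD we will also collect CSF for biomarkers". Evaluable pairs may therefore be well below 20 per arm, especially for CSF. Assumed: equal SD (sigma) before and after, before-after correlation rho of 0.3 to 0.8, and 10 or 20 pairs per arm.

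**3. Variance per patient of the between-arm comparison.**

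- t-test on the later value: sigma²
- t-test on the change score: 2(1 − rho) sigma²
- ANCOVA on the earlier value: (1 − rho²) sigma²

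Detectable difference at 80% power, in SD units: (1.960 + 0.842) × √(2/n) × √(variance factor). For the later value alone this is 2.802 × √(2/20) = 0.89 with 20 per arm and 2.802 × √(2/10) = 1.25 with 10 per arm. With ANCOVA these are multiplied by √(1 − rho²):

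| rho | 1 − rho² | Variance reduction | ANCOVA, 20/arm | ANCOVA, 10/arm | Change-score factor 2(1 − rho) |
|---|---|---|---|---|---|
| 0.3 | 0.91 | 9% | 0.85 | 1.20 | 1.40 |
| 0.5 | 0.75 | 25% | 0.77 | 1.09 | 1.00 |
| 0.7 | 0.51 | 49% | 0.63 | 0.89 | 0.60 |
| 0.8 | 0.36 | 64% | 0.53 | 0.75 | 0.40 |

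To match ANCOVA at 20 per arm, the unadjusted test would need 20/0.91 = 22 per arm at rho 0.3 and 20/0.75 = 27 at rho 0.5. A t-test on change is worse than the unadjusted test when rho is below 0.5, so subtracting the earlier value is not a substitute for adjusting for it.

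**4. Validity check by simulation** (normal data, 20 per arm; 10,000 trials for the t-test, 3,000 for ANCOVA; rho 0.3, 0.5, 0.7). With no effect, the t-test on later values rejected in 5.1% to 5.2% of trials and ANCOVA in 5.3% to 5.6%. With a true difference of 0.8 SD, both had a mean estimate of 0.80. The SD of the estimate was 0.32 for the t-test and 0.31, 0.28 and 0.23 for ANCOVA. The squared ratios are 0.95, 0.79 and 0.53, against 0.91, 0.75 and 0.51 by formula; the shortfall reflects the estimation of a slope from 40 patients, and simulation error. Power was 69% to 70% for the t-test and 72%, 80% and 92% for ANCOVA.

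**The case against.** The strongest case on the other side is that little is lost. Section 3 of the protocol frames these endpoints modestly, "Secondary endpoints include descriptive comparisons between the active and sham treatment groups in", in a pilot with no formal hypotheses, so power has limited weight. That is fair, and it keeps the point modest. It does not remove it: the SAP tests these variables at 0.05, and a descriptive estimate of change also needs the two samples linked.

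Several stronger readings are tempting, and the documents do not support them.

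- *The pre-stimulation sample is never used.* The SAP's general rule allows a summary of change from baseline, and the sample would itself be t-tested if its time counts as a visit. The SAP also does not say whether the t-test is on the level or the change.
- *Active versus sham is left unanswered or biased.* Under randomisation the t-test on later values is unbiased and keeps its error rate. Chance imbalance in the first sample is already covered by that error rate.
- *The data are skewed, and blood and CSF will be pooled.* Neither document gives a distribution, and a list joining the two fluids does not say that they will be combined.
- *Transcranial Doppler has the same defect.* Section 8.1 says that "we will assess the changes in transcranial velocities around the time of the stimulation of the Vagus nerve", but the listed endpoint in both documents is velocity compared between arms, which a between-arm test matches.

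One objection bears on the remedy and stands. The section 3 table puts the first sample ahead of the first stimulation, whereas section 8.1 puts it ahead of the 11:30 am session, the second of the four daily times in sections 4.4 and 6.1.2. If stimulation has already begun, adjusting for that sample could remove part of the effect. The sampling time must be settled before the covariate is defined.

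**Conclusion.** The point holds as a gap in specification with a cost in precision. The before/after part of the biomarker endpoint has no inferential method, and its descriptive summary rests on a baseline that may not be the intended sample. The active-versus-sham comparison is valid but wider than necessary: adjustment would cut its variance by about 9% at rho 0.3 and 64% at rho 0.8. At 20 pairs per arm the detectable difference would fall from 0.89 SD to between 0.85 and 0.53 SD.

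These sizes rest on assumed correlations, equal SDs and an assumed number of pairs. At the low end of the range the gain is small. The specification gap rests on the text alone. The change should be made, but the primary analysis does not depend on it.

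**What to change.** In the SAP section on secondary and exploratory variables:

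- Name the sample drawn before the patient's first stimulation as the biomarker baseline, and reconcile the sampling time in protocol sections 3 and 8.1 with it. A sample taken after stimulation has begun should not serve as the covariate.
- Replace the t-test for cytokines and permeability markers with ANCOVA of the 24 h value on arm and that baseline. If the day 5 and day 7 samples are to be included, use a baseline-adjusted mixed model and name the time point of interest.
- Fit blood and CSF separately. Use the log scale if the data are skewed.
- Report the between-arm estimate with a 95% CI, as a ratio if logged.

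The cost is SAP wording and one clarification of sampling time in the protocol; no further samples are needed. Patients lacking one of the two samples drop out of the ANCOVA unless a mixed model is used, and a little precision is lost if the correlation is near zero.
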